8.2. Setting

The Hepatitis C Therapeutic Registry and Research Network is a consortium of more than 103 academic and community investigators enrolling patients treated with i-HCV regimens with direct acting agents. The first patient was enrolled on November 11, 2011. As of January 2014, 2845 patients have been enrolled in 103 U.S. sites. There is one site in Puerto Rico. Germany will be activated for enrollment in mid February 2014 with 2 sites. Discussion is underway to include one center each in the UK, France, Israel, Spain, and Canada. A list of participating sites is available on the website at <http://www.hcvtarget.org/index.php/about-us/hcv-target-investigators-and-sites>. Centers are both academic (59 sites) and community (44 sites) and primarily are hepatology practices. The visit frequency is defined by local standard of care. Long term follow-up was added in a September 2013 protocol amendment and includes 3-year follow-up on patients that continue to return to the center as part of their local standard of care.

The data in the registry is of published high quality [[name], 2013]. The Clinical Coordinating Center (CCC) resides at the University of Florida (PI: [name]) and the Data Coordinating Center (DCC) resides at the University of North Carolina at Chapel Hill (PI: [name]).

HCV-TARGET utilizes a novel, standardized, centralized source data abstraction core to abstract data from de-identified clinical source records provided from participating sites. Demographic, clinical, adverse event, virological, and long-term post treatment follow-

up, including co-morbid conditions, complications related to liver disease, mortality, and AEs, are obtained and subsequently verified by a separate monitoring team housed at the Data Coordinating Centre. Members of the data abstraction team are highly trained and quality control practices, including the development of standardized chart data abstraction conventions pertinent to clinically-based, real-world records have been implemented to ensure data quality, consistency, and error reductions.

For the eltrombopag cohort study nested within HCV-TARGET, users of eltrombopag will be identified and included. The study will be observational and non-interventional.

8.3. Variables

Variables included in this study are summarized below:

8.3.1. Outcomes

The main outcomes of this study are:

- Hepatic decompensation, defined as new onset or worsening of baseline of any of the following:
 - Ascites
 - Hepatic encephalopathy
 - Variceal Bleeding
- Thromboembolic events
 - Myocardial infarction (MI)
 - Ischemic Stroke (IS)
 - Portal vein thrombosis (PVT)
 - Deep vein thrombosis (DVT)
 - Pulmonary embolism (PE)
- Mortality (all cause and cause-specific)
- Treatment effectiveness among eltrombopag users, assessed as
 - Percentage of eltrombopag users able to initiate antiviral therapy
 - Percentage of eltrombopag users requiring no, one, two, three, or four or more interferon dose reductions
 - Percentage of eltrombopag users reaching early virologic response, defined as clinically significant reduction in HCV RNA (≥ 2 log₁₀ drop or undetectable) after 12 weeks of antiviral treatment
 - Percentage of eltrombopag users achieve SVR, defined by HCV RNA negative 24 weeks after cessation of treatment
 - Change in platelet counts before and during antiviral therapy among those able to initiate antiviral therapy

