3. ABSTRACT

***Title** A prospective observational cohort study nested within the Hepatitis C Therapeutic Registry and Research Network (HCV-TARGET) to evaluate real world use of eltrombopag in adult patients with chronic hepatitis C virus infection who are unable to initiate or maintain optimal interferon-based therapy due to thrombocytopenia.

***Rationale and background.** Hepatitis C Virus (HCV) is a leading cause of chronic liver disease worldwide. Treatment consists of combination therapy with peginterferon and ribavirin (double therapy) or where appropriate, interferon, ribavirin and a direct acting anti-viral agent (triple therapy), although the treatment landscape is changing rapidly with new therapies. Thrombocytopenia as an interferon-related adverse event or a complication of chronic liver disease often necessitates dose reduction and discontinuation of interferon-based therapy in these patients.

Eltrombopag (Revolade™/Promacta™) is an oral second generation thrombopoietin receptor agonist which promotes megakaryocyte differentiation and proliferation. Eltrombopag (Promacta) was approved in the U.S. in November 2012 for chronic hepatitis C virus (HCV)-associated thrombocytopenia to allow for the initiation and maintenance of interferon-based therapy. Eltrombopag (REVOLADE) was approved by the European Commission in September 2013 for the treatment of thrombocytopenia in adult patients with HCV, where the degree of thrombocytopenia is the main factor preventing the initiation or limiting the ability to maintain optimal interferon-based therapy. Eltrombopag allows patients who would otherwise have been poor candidates due to low platelet counts to undergo interferon-based therapy for HCV.

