7. RESEARCH QUESTION AND OBJECTIVE(S)

The primary objective of this study is to report the incidence of hepatic decompensation in patients with chronic hepatitis C virus infection who receive eltrombopag therapy with interferon-based therapy that also includes direct acting anti-viral agents, a group not studied in the Phase III randomized clinical trials. Secondary objectives include reporting the real-world incidence of thromboembolic events and mortality and identifying risk factors for hepatic decompensation, thromboembolic events and mortality in this group of understudied patients. The study will also report the 3-year incidence of hepatic decompensation and mortality, comparing patients who achieve sustained virologic response to patients who do not achieve SVR among eltrombopag patients treated with interferon-based therapy and direct acting agents, which has not yet been studied. The study will also examine effectiveness of eltrombopag to initiate and maintain HCV therapy and achieve EVR and SVR among patients specifically using direct-acting anti-virals with interferon-based therapy.

Specific Study Aims

- Primary: Determine the incidence of hepatic decompensation among patients receiving eltrombopag with interferon-based therapy and direct acting anti-viral agents,
Secondary:
- Determine the incidence of thromboembolic events and mortality among patients receiving eltrombopag with interferon-based therapy and direct acting anti-viral agents
 - Explore factors associated with risk of hepatic decompensation and risk of thromboembolic events among patients receiving eltrombopag with interferon-based therapy and direct acting anti-viral agents
 - Determine the incidence rate ratio of hepatic decompensation and mortality at 3 years, comparing eltrombopag patients achieving sustained virologic response to eltrombopag patients who did not achieve SVR in the setting of treatment with interferon-based therapy and direct acting anti-viral agents
 - Obtain information on treatment effectiveness among patients receiving eltrombopag with interferon-based therapy and direct acting anti-virals with respect to initiating, maintaining and completing HCV therapy, and achieving EVR and SVR

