8. RESEARCH METHODS

8.1. Study Design

The HCV-TARGET study is a carefully maintained longitudinal observational research registry to prospectively enrol and follow HCV patients treated with anti-HCV regimens in a real-world setting in order to rapidly inform strategies for better management of populations underrepresented in clinical trials, identify and remediate gaps in treatment

guidelines and adverse event management in order to optimize rates of SVR. It's comprised of patients that receive HCV therapy with direct acting antiviral agents. All adult patients (age 18 or older) who are prescribed HCV treatment with direct acting antiviral agents outside of a clinical trial are eligible for participation, provided they provide written informed consent and are not participating in any other registry or study where HCV treatment outcomes are reported, except where approved or conducted as an adjunct project of the HCV-TARGET registry.

This study is an eltrombopag cohort study nested within HCV-TARGET, comprising all patients treated with eltrombopag. Nesting the eltrombopag cohort study within the HCV-TARGET is an efficient way to identify and study eltrombopag users in a real-world setting. All patients treated with eltrombopag will be included in the nested cohort study. No patients who have not been exposed to eltrombopag will be included in the nested cohort study. Within the nested cohort study, patients will be followed for up to three years after eltrombopag initiation. The major safety outcome is hepatic decompensation. Incidence of thromboembolic events and mortality will also be determined. Thromboembolic events include myocardial infarction, ischemic stroke, pulmonary embolism, deep vein thrombosis, portal vein thrombosis, and other events. The major effectiveness outcomes include ability to initiate anti-viral therapy, ability to maintain anti-viral therapy, early virologic response and sustained virologic response. The incidence of hepatic decompensation and of mortality at three years will be compared between eltrombopag users who achieve SVR and those users who do not achieve SVR. An interim analysis will be conducted in 2016 and the final analysis will be completed in 2018.

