8.3.2. Exposure

- The main exposure variable is Treatment with eltrombopag, including dose, duration of treatment, drug discontinuation, In combination with peginterferon, ribavirin, and direct acting antiviral agents (triple therapy)

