9. PROTECTION OF HUMAN SUBJECTS

9.1. Ethical approval and subject consent

The HCV-TARGET protocol and informed consent documents received approval by the local site IRB prior to initiation of the study at each site. Consent for participation in HCV-TARGET includes permission 1) to submit de-identified historical medical records related to patient demographics, medical/co-morbid condition history, prior HCV therapy and evaluation of liver disease, 2) to submit prospective de-identified medical records related to HCV treatment response, safety, side effects, side effect management and safety/efficacy outcomes of antiviral therapy; 3) for collection of biospecimens including genomic DNA to be archived for future studies (optional); and 4) to be followed for HCV co-morbid conditions and mortality for up to 3 years after treatment outcome is determined.

Written informed consent must be obtained before any data collection and may be given by patients after being prescribed HCV treatment up to 4 weeks after treatment initiation. The method of obtaining and documenting the informed consent and the contents of the consent complies with ICH GCP guidelines and all applicable laws and regulations.

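### Initiation and maintenance, two of the five effectiveness outcomes in 8.3.1, are defined so that they tend to overstate success, and completion has no outcome

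*Protocol*

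**What the plan says.** The last secondary aim in Section 7 is effectiveness "with respect to initiating, maintaining and completing HCV therapy, and achieving EVR and SVR". Section 8.3.1 turns this into five items: initiation, interferon dose reductions, early virologic response (EVR), sustained virologic response (SVR) and change in platelet count.

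- Initiation is the "Percentage of eltrombopag users able to initiate antiviral therapy".
- Maintenance appears only as the "Percentage of eltrombopag users requiring no, one, two, three, or four or more interferon dose reductions". There is no item for stopping interferon or for completing the course.
- The platelet item is limited to patients able to start antiviral therapy. The dose-reduction item has no such limit, so its denominator is all eltrombopag users.

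The Abstract says that thrombocytopenia "often necessitates dose reduction and discontinuation of interferon-based therapy in these patients", so it names two consequences. In Section 8.3.2 the wording "including dose, duration of treatment, drug discontinuation" describes eltrombopag as the exposure; it is not an interferon outcome.

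On entry to the registry, Section 8.1 states: "All adult patients (age 18 or older) who are prescribed HCV treatment with direct acting antiviral agents outside of a clinical trial are eligible". Section 8.2 describes the network as "enrolling patients treated with i-HCV regimens with direct acting agents". Under Section 9.1, consent "may be given by patients after being prescribed HCV treatment up to 4 weeks after treatment initiation". Section 8.9 counts it as a strength that every eltrombopag user in the registry is included, and concludes from this that selection bias is minimised.

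**The concern.** A measure of maintenance should get worse when more patients lose their treatment. This one need not: someone who goes straight from full-dose interferon to none never has a reduction to count. The measure picks up the milder of the two consequences named in the Abstract and misses the more serious one.

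A measure of the ability to initiate needs a denominator of patients who were given eltrombopag so that they could start. Here, a patient whose platelet count never rose enough for HCV treatment to be prescribed cannot enter the registry. Two groups that can enter count as successes whatever eltrombopag did: those who consent after their first antiviral dose, and those who began eltrombopag during antiviral therapy.

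Both percentages will go to regulators as effectiveness results of an uncontrolled cohort, with no comparison group to reveal the distortion.

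**Working it through.** The protocol states no target rate, precision or power for initiation or maintenance, so there is no figure of its own to reproduce on this point. The one input it supplies is the projected cohort in Section 8.5: 5000 × 2.1% = 105 users. It gives neither a rate of stopping interferon nor a rate of failing to initiate. The rates below are assumptions, chosen only to show how the definitions behave.

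**Maintenance.** Let r be the share with at least one reduction and d the share who stop interferon with no earlier reduction.

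- Reported as no reductions: 1 − r.
- Neither reduced nor stopped: 1 − r − d.
- Overstatement: (1 − r) − (1 − r − d) = d, whatever r is.

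With r = 30% (assumed), the reported figure is 70% throughout:

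| d (assumed) | Neither reduced nor stopped | Stoppers counted as no reductions, of 105 |
|---|---|---|
| 10% | 60% | 10.5 |
| 20% | 50% | 21 |
| 30% | 40% | 31.5 |

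Users who receive no interferon add to the same category. They can be in the cohort because registry entry requires a DAA, not interferon, and every eltrombopag user is included.

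**Initiation, selection into the registry.** Let f be the true share of eltrombopag starters who never initiate, and c the chance that such a patient is enrolled relative to one who initiates.

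- Observed initiation = (1 − f) / [(1 − f) + f × c].
- f = 20%, c = 0.10: 0.80 / (0.80 + 0.02) = 97.6%.

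| f (assumed) | True rate | c = 0 | c = 0.10 | c = 0.25 | c = 1 |
|---|---|---|---|---|---|
| 5% | 95% | 100% | 99.5% | 98.7% | 95% |
| 10% | 90% | 100% | 98.9% | 97.3% | 90% |
| 20% | 80% | 100% | 97.6% | 94.1% | 80% |
| 30% | 70% | 100% | 95.9% | 90.3% | 70% |

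The bias disappears only at c = 1, that is, if failures enter the registry as readily as successes. The entry condition in Section 8.1 prevents that for anyone never prescribed HCV treatment.

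**Initiation, order of treatments.** Let m be the share of the cohort who began eltrombopag after antivirals had started, and p the initiation rate among the rest. The reported rate is m + (1 − m) × p, which exceeds p whenever m > 0 and p < 1. The study title includes patients unable to maintain interferon, so m should not be taken as zero.

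**The case against.** The strongest reply is that Section 8.3.1 contains no rule scoring stoppers as successes. It lists a distribution in a section that summarises variables, and the handling of stoppers and non-starters could be settled in a statistical analysis plan that is not at hand. The Abstract and Section 8.1 name the ability to maintain therapy in general terms, and Section 8.7 promises a description of antiviral therapy over time. This stands in part: an analysis plan could add a discontinuation table. But Section 8.3.1 is the only place that makes maintenance measurable, it leaves out something Section 7 sets as an aim, and taken literally it gives a stopper a count of zero. No analysis plan can recover patients who never entered the registry.

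A reader might infer that the initiation rate is close to 100% by construction. The documents do not support that. Eligibility rests on prescription and consent may precede the first dose, so a patient who is prescribed treatment, consents and never starts can be enrolled as a failure. The share consenting late is unknown.

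A reader might also infer that eltrombopag's effectiveness as a whole will look too good. That goes too far. EVR and SVR are percentages of eltrombopag users and can record early stoppers as failures if these stay in the denominator.

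There is also some tension in saying that non-starters are mostly missing from the cohort and that they swell the zero-reduction group. The maintenance problem therefore rests mainly on patients who stop, and on users of interferon-free regimens, rather than on non-starters.

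Finally, effectiveness is the last secondary aim of a descriptive safety study, and no test or decision rule depends on these percentages. That limits the consequence but leaves the definitions unsound.

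**Conclusion.** The concern holds for two of the five effectiveness outcomes. Both tend to overstate success, and the direction follows from the text. As a measure of maintenance, the no-reduction share is too high by the share of users who stop interferon without an earlier reduction or receive none. The initiation share is conditional on HCV treatment having been prescribed and counts some users who had started before eltrombopag or before consent. The completion aim has no outcome.

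The size cannot be derived from the documents. The illustrations (10 to 20 points for maintenance at an assumed 10% to 20% stopping; a true 80% initiation shown as 94.1% to 100% for c between 0.25 and 0) simply follow their assumptions and are not estimates. The primary outcome, hepatic decompensation, is not affected. The definitions should be corrected before the interim report.

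**What to change.** 1. In Section 8.3.1, report interferon dose reductions among interferon initiators only, in exclusive categories, with early permanent discontinuation of interferon as a category of its own.
2. Add completion as an outcome, defined as completion of the course intended by the treating clinician. The reference has to be that course because Section 8.4 says the registry sets no regimen or duration.
3. Report initiation only for users who started eltrombopag and gave consent before the first antiviral dose, and state that it is conditional on HCV treatment being prescribed.
4. Qualify the selection-bias statement in Section 8.9: including every user in the registry does not deal with selection into the registry.

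The source material is largely in hand. Section 8.4 lists regimen and dose adjustments, and Section 8.6 says that all clinic notes are submitted. Interferon stop dates are not named as a collected item, since the discontinuation in Section 8.3.2 refers to eltrombopag, so some extra abstraction is needed. The other costs are a less favourable maintenance figure and a smaller denominator, hence a wider interval, for initiation.

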TITLE PAGE

Division: Worldwide Development

Information Type: Worldwide Epidemiology Study Protocol

Title:	A prospective observational cohort study nested within the Hepatitis C Therapeutic Registry and Research Network (HCV-TARGET) to evaluate real world use of eltrombopag in adult patients with chronic hepatitis C virus infection who are unable to initiate or maintain optimal interferon-based therapy due to thrombocytopenia.
---------------	---

Compound Number: SB-497115

Development Phase IV

Effective Date: 12-AUG-2014

Subject: Hepatitis C Virus, Thrombocytopenia, Cohort study

Author(s): [REDACTED]

PASS information

Title	A prospective observational cohort study nested within the Hepatitis C Therapeutic Registry and Research Network (HCV-TARGET) to evaluate real world use of eltrombopag in adult patients with chronic hepatitis C virus infection who are unable to initiate or maintain optimal interferon-based therapy due to thrombocytopenia.
Protocol version identifier	02
Date of last version of protocol	20-MAR-2014
EU PAS register number	To be registered after PRAC approval
Active substance	Eltrombopag
Medicinal product	Eltrombopag
Product reference	SB-497115-GR
Procedure number	Not applicable
Marketing authorisation holder(s)	GlaxoSmithKline Trading Services Limited [name] Country: Ireland Telephone: [REDACTED]
Joint PASS	No
Research question and objectives	The primary objective of this study is to report the incidence of hepatic decompensation in a real-world setting in patients with chronic hepatitis C virus infection who receive eltrombopag therapy with interferon-based therapy that also includes direct acting anti-viral agents, a group not studied in the Phase III randomized clinical trials. Secondary objectives include reporting the real-world incidence of thromboembolic events and mortality and identifying risk factors for hepatic decompensation, thromboembolic events and mortality in this group of understudied patients. The study will also report the 3-year incidence of hepatic decompensation and mortality, comparing patients who achieve sustained

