***Data analysis**

Cumulative incidence rates and corresponding 95% confidence intervals as well as Kaplan-Meier rates and corresponding 95% confidence intervals will be calculated for the occurrence of hepatic decompensation, thromboembolic events, or mortality, as separate events, at multiple time points during and at the end of the 3-year follow-up period. Baseline factors potentially predictive of events will be identified through Kaplan-Meier survival estimates for patients with vs. without the factor and testing for statistical significance using the log-rank test. Cox proportional hazards models will be constructed to evaluate the influence of these identified factors simultaneously.

Patient demographics and characteristics will be described at the time of initiation of eltrombopag. Virology, laboratory information, information on dose and duration of eltrombopag, early and sustained virologic response, anti-viral therapy and incidence of hepatic decompensation and thromboembolic events will be described at baseline and distinct follow-up time points. Continuous variables will be reported as mean, standard deviation, median, 25th and 75th quartiles, and range. Categorical variables will be summarized as number and proportion of subjects with observed (non-missing) data, with corresponding 95% confidence intervals (CI) by exact methods.

The number and percentage of patients who achieve early virologic response and sustained virologic response will be reported at distinct follow-up time points. The probability of attaining EVR and SVR by these time points will be presented as Kaplan-Meier estimates, along with median time to attaining virologic response.

***Milestones.** An interim analysis will be conducted in 2016 and the final analysis will be completed in 2018.

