8.7. Data analysis

The eltrombopag cohort study nested within HCV-TARGET is a descriptive study conducted to provide primarily incidence of hepatic decompensation and secondarily other important outcomes such as thromboembolic events and mortality in HCV patients who are treated with direct acting anti-viral agents as part of their interferon-based regimen, a group of patients not previously studied in the randomized clinical trials. Cumulative incidence rates will be calculated for the occurrence of hepatic decompensation, thromboembolic events, or mortality, as separate events, at multiple time points during the study and at the end of the 3-year follow-up period. The 95% CIs for cumulative incidence will be calculated using the method outlined by Newcombe et al [Newcombe, 1998]. Baseline factors potentially related to each event will be identified during exploratory analyses by comparing Kaplan-Meier survival estimates for patients with vs. without the factor and testing for statistical significance using the log-rank test. Cox proportional hazards models will be constructed to evaluate the influence of these identified factors simultaneously.

Kaplan-Meier survival estimates will be calculated for the outcomes of hepatic decompensation, thromboembolic events, and all-cause mortality. Thromboembolic events will be presented as a single category as well as grouped by venous or arterial origin, and by individual event types. Confidence intervals for survival rates will be calculated using the method outlined by Simon et al [Simon, 1986]

Patient demographics and characteristics will be described at the time of initiation of eltrombopag. Virology, laboratory information, information on dose and duration of eltrombopag, early and sustained virologic response, anti-viral therapy and incidence of hepatic decompensation and thromboembolic events will be described at baseline and distinct follow-up time points. Continuous variables will be reported as mean, standard deviation, median, 25th and 75th quartiles, and range. Categorical variables will be summarized as number and proportion of subjects with observed (non-missing) data, with corresponding 95% confidence intervals (CI) by exact methods.

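### EVR at antiviral week 12 is counted as an effectiveness outcome for all eltrombopag users, although for users who start eltrombopag after week 12 the reading precedes exposure

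*Protocol*

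**What the plan says.** Four statements in the protocol bear on this point.

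- **Who enters.** Section 8.1: "All patients treated with eltrombopag will be included in the nested cohort study". No section sets a limit on when eltrombopag starts relative to antiviral therapy. The title describes patients "who are unable to initiate or maintain optimal interferon-based therapy due to thrombocytopenia", so users already on antivirals belong to the target population.
- **Time zero and baseline.** Section 8.1: "patients will be followed for up to three years after eltrombopag initiation". Section 8.7: "Patient demographics and characteristics will be described at the time of initiation of eltrombopag".
- **EVR.** Section 8.3.1, under treatment effectiveness: "Percentage of eltrombopag users reaching early virologic response, defined as clinically significant reduction in HCV RNA". The criterion is a drop of at least 2 log10 or undetectable RNA, read "after 12 weeks of antiviral treatment".
- **Use made of EVR.** Section 8.1 names it among the major effectiveness outcomes. Section 7 says the study will examine how effective eltrombopag is in achieving it.

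The abstract adds a time-to-event analysis: "The probability of attaining EVR and SVR by these time points will be presented as Kaplan-Meier estimates". Section 8.7 plans that analysis for SVR only.

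**The concern.** Cohort membership and follow-up run on the eltrombopag clock, while EVR runs on the antiviral clock. The two agree well enough for a patient who takes eltrombopag in order to begin antivirals. They come apart for a patient who adds it during therapy. If the first dose falls after antiviral week 12, the EVR result was settled before exposure began, yet section 8.3.1 still counts it in a percentage presented as effectiveness among eltrombopag users.

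Such a patient also had to be on antiviral therapy at week 12 in order to become a late starter. Patients who stopped earlier had no chance to enter by this route. That selection could favour responders, so the pooled percentage may depend partly on how many users started late.

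**Working it through.** **Step 1. Do the rules admit late starters?** Yes. Entry requires only eltrombopag use (8.1). The title and the European indication in 6.1 cover difficulty maintaining therapy as well as initiating it. The abstract describes thrombocytopenia as an adverse event of interferon, so it can arise on treatment. Section 8.4 records concomitant medications both at baseline and on treatment.

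**Step 2. What does the EVR rule do with them?**

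| First eltrombopag dose | Exposure before the week-12 reading | Counted under 8.3.1 |
|---|---|---|
| Before antivirals | Throughout the 12 weeks, if continued | Yes |
| Between antiviral start and week 12 | Part of the 12 weeks | Yes |
| After week 12 | None | Yes |

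The third row is the problem. The second row is only partly attributable to exposure.

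**Step 3. The plan's own denominator.** 2.1% of 5000 = 0.021 × 5000 = 105 users, as stated in section 8.5. The observed fraction, 58/2707 = 2.14%, agrees.

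**Step 4. Illustration.** Let f be the share starting after week 12, a the EVR rate in the other users and b the EVR rate in late starters. Then:

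- pooled EVR = (1 − f) × a + f × b
- shift = f × (b − a)
- users credited with a pre-exposure response = 105 × f × b

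The protocol gives none of f, a or b. All values below are assumed.

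| f | a | b | Pooled EVR | Shift (points) | Pre-exposure EVRs of 105 |
|---|---|---|---|---|---|
| 20% | 60% | 90% | 48 + 18 = 66% | +6 | 18.9 |
| 40% | 60% | 90% | 36 + 36 = 72% | +12 | 37.8 |
| 20% | 60% | 80% | 48 + 16 = 64% | +4 | 16.8 |
| 20% | 60% | 50% | 48 + 10 = 58% | −2 | 10.5 |
| 10% | 70% | 70% | 63 + 7 = 70% | 0 | 7.35 |
| 50% | 50% | 95% | 25 + 47.5 = 72.5% | +22.5 | 49.9 |

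Over f = 10–50%, a = 50–70% and b = 70–95%, the shift runs from 0 to +22.5 points, and about 7 to 50 users are credited with a pre-exposure response. Those ranges never put b below a, so they cannot show a downward shift. The fourth row lies outside them and shows that the sign follows b − a.

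**Step 5. Two quantities to keep apart.** In the first row the shift is 6 points, but the part of the pooled figure made up of pre-exposure responses is 0.20 × 90% = 18 points. In the second row the two are 12 and 36 points. Even with no shift, the pre-exposure responses remain in the numerator.

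**The case against.** The strongest reply is that the study is descriptive and has no unexposed group, and that EVR is by nature a property of the antiviral course. On that view the percentage of users with EVR is a legitimate cohort description, misleading only if read as an effect of eltrombopag. This is right as far as it goes, but sections 7 and 8.1 invite that reading by placing EVR under the effectiveness of eltrombopag.

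Second, section 8.7 also describes virologic response at baseline. If baseline means eltrombopag initiation, EVR already present at entry would be visible. It would still not leave the percentage in 8.3.1.

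Third, analysis by timing of start could be left to a statistical analysis plan. A split could be. But section 8.3.1 itself fixes the population, the criterion and the clock, and the point concerns what it fixes.

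A reader might infer three stronger things that the protocol does not support:

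- **That EVR is biased upward by a known amount.** Selection makes this plausible, but there are no data on f, a or b.
- **That EVR cannot be derived at all for late starters.** The undetectable criterion needs no reference value, section 8.4 lists viral load among the registry's baseline factors, and no section measures the drop from eltrombopag initiation.
- **That it is enough to restrict EVR to users with a week-12 sample taken after the first dose.** Read literally, that would remove users who never start antivirals or stop early, and dropping early failures would itself inflate EVR.

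**Conclusion.** The point stands as a flaw in the outcome definition. For users who start eltrombopag after antiviral week 12, the EVR counted in section 8.3.1 precedes exposure and says nothing about eltrombopag. This follows from the entry rule and the EVR clock and needs no numerical assumption.

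The size and direction of any distortion are unknown. The example of 60% moving to 66%, with about 19 of 105 users credited before exposure, rests on three assumed inputs. If few users start late, the effect is small.

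The weight is moderate. EVR is one part of a secondary aim, with no hypothesis test or sample-size calculation attached. The primary objective, incidence of hepatic decompensation, is not touched. SVR is less exposed because it is read 24 weeks after treatment ends.

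**What to change.** In sections 8.3.1 and 8.7:

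1. Base the EVR effectiveness percentage on users whose first eltrombopag dose came before antiviral week 12.
2. Keep in that denominator, as non-responders, users who never start antivirals, who stop before week 12, or who have no week-12 sample because they stopped.
3. Take the log10 drop from the last HCV RNA before antiviral start.
4. Report users who started eltrombopag after week 12 separately, outside the effectiveness percentage.
5. Show EVR by eltrombopag start before antivirals versus between antiviral start and week 12.
6. If the Kaplan-Meier analysis of EVR in the abstract is kept, apply the same restriction so that no event falls before time zero, and bring the abstract and section 8.7 into agreement.

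The change is one of wording and analysis. Regimen, concomitant medication and virology data are already abstracted (8.2, 8.4), and section 8.8 provides for eltrombopag-specific data forms.

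The price is precision. With the assumed 20% late starters, the denominator falls from 105 to 105 − 21 = 84. By the normal approximation at 60% EVR, the 95% half-width rises from 1.96 × √(0.24/105) = 9.4 points to 1.96 × √(0.24/84) = 10.5 points.
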